trauma is known to be misclassified, with consequent under-reporting of injuries affecting the anal sphincter complex (10).

Risk factors for severe perineal trauma (grade III-IV) are giving birth vaginally for the first time, having an assisted vaginal birth, giving birth vaginally after a previous caesarean section, or giving birth to a baby that weighs more than 4000g, and the risk increases with age (1, 11-13). Some of the midwifery care methods used to prevent perineal injuries have been evaluated in clinical trials but there are still gaps in our knowledge (14). Even if scientific evidence is lacking for most of the preventive strategies used by midwives except for warm compresses held at the perineum (14), midwives believe that a slow and controlled birth is a key factor in prevention. Several studies indicate that a combination of strategies can be effective in preventing perineal trauma (4, 15-17). Giving birth is a profound experience for the woman and her partner and an experience that has significance for the woman all her life (18). The second stage is considered to be the most stressful part of the labor for the woman and her unborn baby, and consequently also for the midwife (19). Despite this, there is still a lack of knowledge about how women experience the second stage and the methods midwives use to facilitate birth and prevent perineal trauma (14). Traditionally midwives have asked colleagues for a second opinion or to assist in complicated situations, or in obstetric emergencies. Recently a new clinical practice has been introduced in approximately 50% of the maternity wards in Sweden to reduce severe perineal trauma (20). This procedure involves two midwives attending the woman during the second stage of labor. The midwife responsible for the birth calls for the second midwife when the active phase of the second stage has started and the presenting part of the baby is visible. The second midwife observes the birth and can assist the midwife responsible for the birth if needed. An unpublished survey from one maternity ward in Sweden showed that most of the midwives appreciated this way of working but were uncertain as to whether it actually reduced the prevalence of severe perineal trauma (20). Furthermore, this clinical practice might have negative side-effects or unintended consequences. The maternity wards that practise this method have not increased the number of midwives. It could be argued that there is a risk that other women in labor will be left unattended for longer periods when two midwives assist at births. How midwives share the responsibility and communicate are factors that needs to be evaluated scientifically.

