
Project design

This is a parallel multicentre randomized controlled trial. Women expecting their first child will be randomized to either having one midwife assisting the active phase of the second stage of labor and the birth of the baby (standard care) or to having two midwives present.

That means that if the woman is randomized to the intervention, the midwife responsible for the birth is assisting the woman as usual but asks a second midwife to be present in the birthing room ready to help her if necessary (intervention). The study is designed according to CONSORT statements (21).

The hypothesis in this study is that the collegial presence of another midwife during the second stage of labor will reduce perineal trauma grade III-IV (primary outcome).

Data from the National Birth Register show that 4.1% of first-time mothers suffered severe perineal trauma in Sweden 2017. The prevalence of severe perineal trauma varies between different regions in Sweden (3). To be able to detect a 50% reduction in severe perineal trauma grade III-IV from 4.1% to 2.0% with 80% power and a 95% level of significance, 1052 women in each group will be needed. The 50% reduction is based on regional figures after a change in practice and is therefore clinically significant. Allowing for a possible drop-out rate of 20% and another drop-out of 20% for possible cases of obstetric emergencies where another midwife will be needed regardless of randomization, this will result in 1473 women in each group and 2946 women in total.

The primary outcome is the prevalence of severe perineal tears grade III-IV.

Secondary outcomes are the prevalence of second-degree tears, vaginal tears, women's experiences of two midwives attending the birth and midwives' experiences of the intervention. Additional secondary outcomes regarding the woman are: the prevalence of episiotomy, first-degree tears, intact perineum (no tear), labial and periurethral tears, postpartum bleeding >500 ml, birth position, instrumental delivery, urinary incontinence, anal incontinence, symptoms of pelvic organ prolapse and sexual function after one year, and self-reported mental health one month and one year after birth. For the one-year follow-up the following validated questionnaires will be used: PFIQ7, PFDI-20, and FSFI and EPDS (22-24). Secondary outcomes regarding the newborn child are: Apgar scores at 1, 5 and 10 minutes, umbilical cord blood gases, and breastfeeding within two hours after birth.

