Inclusion criteria: Swedish speaking women expecting their first child or with a prior caesarean section opting for a vaginal birth, with a singleton live foetus in cephalic presentation from gestational week 37+0.

Participating clinics: The maternity ward at Karolinska University Hospital Huddinge and Solna, and the maternity wards at SUS Malmö and Lund. With four participating clinics the time for patient recruitment will be shortened and this will also increase the generalizability of the results.

Randomization process: It will not be possible to blind either women or midwives in this study. The participants will be randomly allocated (1:1) to the intervention group (collegial presence of another midwife during the second stage) or to the standard care group (one midwife is responsible for the care during the second stage). Randomization will take place at the start of the second stage. To allow for equal distribution between the groups, block randomization in blocks of ten will be used. The midwife in charge will be responsible for the randomization process. Sealed and opaque envelopes will be used and will be prepared with a unique code consisting of a first code letter identifying each study site, a second code letter identifying which group it belonged to (intervention or control) followed by a consecutive number.

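### The design paragraph and the planning rate cover first-time mothers only, but the inclusion criterion also admits women with a prior caesarean and does not say whether an earlier vaginal birth is allowed

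*Protocol*

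**What the plan says.** Three places in the protocol bear on who is studied, and one on how differences between participants are handled.

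- **Project design, opening paragraph:** "Women expecting their first child will be randomized to either having one midwife assisting the active phase of the second stage of labor". Prior caesarean is not mentioned.
- **Project design, sample size:** "Data from the National Birth Register show that 4.1% of first-time mothers suffered severe perineal trauma in Sweden 2017". The target is a fall to 2.0%, "with 80% power and a 95% level of significance, 1052 women in each group will be needed". No rate or expected share is given for women with a prior caesarean.
- **Project design, inclusion criteria:** "Swedish speaking women expecting their first child or with a prior caesarean section opting for a vaginal birth", with further conditions on number of fetuses, presentation and gestational age. Nothing is said about earlier vaginal births.
- **Background, risk factors for grade III-IV trauma:** the list includes "giving birth vaginally for the first time, having an assisted vaginal birth, giving birth vaginally after a previous caesarean section". No rates are attached.

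The Analysis section commits to adjusting for study site by logistic regression. Other baseline variables enter only if randomisation leaves them unbalanced.

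**The concern.** A woman with a prior caesarean is not ordinarily expecting her first child, so the design paragraph and the inclusion criterion disagree on who is randomised. Nothing elsewhere in the document reconciles them.

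The difference matters for the primary outcome on the protocol's own account. Read literally, the criterion admits three groups:

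1. first-time mothers;
2. women with a caesarean and no vaginal birth, who carry both of the listed factors;
3. women with a caesarean and an earlier vaginal birth, who lack the first-vaginal-birth factor but still fall under vaginal birth after caesarean.

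The 4.1% belongs to the first group alone and is not described as standing in for the mixture. At stake are a clear statement of the population to which the result applies, a planning rate that matches it, and the handling of a prognostic factor that is known before the trial starts.

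**Working it through.** **Step 1: reproduce the plan's figure.** Inputs from the sample size paragraph: p1 = 0.041, p2 = 0.020, power 80%. The stated 95% level of significance is read as two-sided alpha 0.05. Allocation is 1:1.

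n per group = [1.960·√(2·p̄(1−p̄)) + 0.842·√(p1(1−p1) + p2(1−p2))]² / (p1−p2)², with p̄ = (0.041 + 0.020)/2 = 0.0305.

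Numerator: (0.4766 + 0.2043)² = 0.4637. Denominator: 0.021² = 0.000441. The ratio is 1051.4, rounded up to **1052**. The plan's figure reproduces exactly, and power at 1052 is 80.0%. The calculation is sound for first-time mothers.

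**Step 2: let the control rate be a mixture.** Let w be the share of added women and r their rate under standard care:

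p1(mix) = (1−w)·4.1% + w·r

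The relative risk is held at 2.0/4.1 = 0.488. The document gives neither w nor r, so every row after the first is an assumption chosen to show a range.

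| w | r | Mixed control rate | n per group for 80% | Power at 1052 |
|---|---|---|---|---|
| any | 4.1% | 4.10% | 1052 | 80.0% |
| 10% | 1% | 3.79% | 1141 | 76.8% |
| 10% | 2% | 3.89% | 1110 | 77.9% |
| 20% | 0.5% | 3.38% | 1283 | 71.8% |
| 20% | 1% | 3.48% | 1245 | 73.1% |
| 10% | 6% | 4.29% | 1004 | 81.8% |
| 20% | 8% | 4.88% | 878 | 86.6% |
| 20% | 10% | 5.28% | 809 | 89.2% |

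Example, fourth row: 0.8 × 4.1% + 0.2 × 0.5% = 3.28% + 0.10% = 3.38%.

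**Step 3: let both kinds of added women enter.** With 5% at 1% and 5% at 8%, the rate is 0.90 × 4.1% + 0.05 × 1% + 0.05 × 8% = 4.14%, and power is about 80%. Offsetting groups largely cancel.

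**Step 4: use the planned recruitment.** The plan randomises 1473 per group. If all contribute to the intention-to-treat analysis, the lowest rate in the table (3.38%) still gives about 85% power under the same relative effect. That figure allows nothing for dilution by emergencies in which a second midwife attends regardless of allocation.

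**The case against.** The strongest reply is that the inclusion criterion is the operative rule and the design sentence only a summary. On that view sites would simply apply the criterion, and the mismatch is editorial. This stands in part: there is no sign that any site would enrol from the summary sentence. It does not answer the silence on earlier vaginal births, which lies in the criterion itself, or the planning rate, which follows the narrower definition.

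A reader might infer that the wider criterion lowers the event rate and leaves the trial underpowered. The document does not support that. Women with both a caesarean and an earlier vaginal birth are only part of the added group, and nothing indicates how many there would be. The Background lists vaginal birth after caesarean as a risk factor without separating out women who have also given birth vaginally. Their rate is therefore not established as lower, and that of the other added women could be higher than 4.1%.

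A reader might also infer that the remedy is to exclude women with an earlier vaginal birth. That goes beyond reconciling the text: the criterion as written admits them, and the choice is the sponsor's.

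On the covariate, it is fair to say that randomisation protects the comparison, that omitting a binary history would not bias it in a trial of this size, and that covariate lists often sit in an analysis plan not shown here. But the protocol does not leave the matter open: its Analysis section fixes a rule that makes adjustment depend on observed imbalance. For a factor the protocol itself calls prognostic, a prior commitment is the better rule.

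**Conclusion.** The contradiction is real and rests on the text alone: the design paragraph and the 4.1% refer to first-time mothers, while the criterion also admits women with a prior caesarean and leaves earlier vaginal births unaddressed. The planning rate is therefore an unlabelled approximation for the enrolled mixture.

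The consequence for power is undetermined. The spread of about 72% to 89% at 1052 per group depends entirely on the assumed shares and rates and on a constant relative risk. It straddles the planned 80%, so it is a measure of what the document leaves unstated and not evidence of a shortfall. The validity of the randomised comparison is not in question. The point is inexpensive to correct and worth correcting, because the result should state clearly to whom it applies.

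**What to change.** 1. Write one population definition and use it in both the design paragraph and the inclusion criteria. It should say explicitly whether a woman with a prior caesarean may also have had an earlier vaginal birth. Which way this goes is for the sponsor to decide.
2. Add a sentence to the sample size paragraph stating that 4.1% is a first-time-mother rate used as an approximation for the enrolled mixture.
3. In the Analysis section, name prior caesarean (yes/no) beside study site as a pre-specified covariate in the adjusted logistic regression for the primary outcome, whatever the observed balance.

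**Cost:** a few sentences and one extra covariate, already available from the eligibility check or the birth record. At the planned rates, 1052 × 0.041 + 1052 × 0.020 gives about 43 + 21 = 64 events. A model with treatment, three indicators for four sites and this covariate has five terms besides the intercept, or about 13 events per term.

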One plus one equals two – Will that do?

A randomized controlled trial to evaluate collegial midwifery practice to prevent perineal trauma

Project plan

2020-02-20

Ethical approval no 2018/476

Purpose and aims

The purpose of this study is to evaluate a clinical practice to reduce severe perineal trauma. This clinical practice involves collegial midwifery assistance during the second stage of labor, where an additional midwife is present during the active phase of the second stage of labor and the birth of the baby. The midwife responsible for the birth is the primary carer of the woman and the other midwife observes the birth or assists the primary midwife if asked to.

Specific aims:

Does the clinical practice with a second midwife present during the second stage and the birth of the baby

- reduce severe perineal trauma (grade III-IV)?
- reduce vaginal tears?
- reduce perineal trauma grade II?
- reduce pelvic floor-related symptoms one year after the birth?
- How do midwives divide work assignments and responsibility between them during the second stage of labor?
- How do women experience having one or two midwives attending the birth of the baby?
- How do women experience midwifery care methods used during the second stage of labor to prevent perineal trauma?

Background

Most women sustain some form of perineal trauma when giving birth vaginally (1). Perineal injuries are classified as grade I-IV (2). A first-degree tear only includes perineal skin or mucosa, whereas a second-degree tear includes muscles in the perineal body. A tear involving a part or the whole of the anal sphincter muscle complex is graded III-IV (2). Data from the Swedish National Birth Register show that 4% of first-time mothers suffered a tear affecting the anal sphincter (3). National registers in Sweden only collect data on severe perineal trauma affecting the anal sphincter but in a recent regional Swedish study 78% of the primiparous women experienced second-degree tears (4). The consequences of second-degree tears and severe perineal trauma are pain (5), dyspareunia (6), and an increased risk of symptomatic pelvic organ prolapse later in life (7). A severe consequence of perineal trauma is anal incontinence, mainly caused by tears affecting the anal sphincter muscle (8, 9). However, second-degree tears may also lead to anal incontinence (8). This may be related to a lack of support from the perineal body due to poor repair. Furthermore, perineal

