Descriptive statistics will be used to present the data. The means, SD, median, quartiles, and 95% CI will be calculated when appropriate as will frequency tables, stratified by the two arms. The primary statistical analysis is intention to treat but a per protocol analysis will also be performed. For comparison between the two groups, t-tests will be used for continuous variables and Chi-square tests for dichotomous variables. A possible preventive effect of having two midwives attending the second stage of labour and birth of the baby will be calculated as a relative risk of severe perineal trauma (tear grade III-IV) with 95% CI. We will adjust for study site using logistic regression. If baseline variables are not balanced by randomisation we will adjust for those using multivariate logistic regression. Response analyses regarding primary outcome will be undertaken at each study centre. Secondary outcomes will be compared using t-tests for continuous variables and Chi-square tests for dichotomous variables. The Mann-Whitney U-test will be used for outcomes based on scores. The project has access to a statistician from Clinical Studies Sweden, Forum South.

Adverse events

As approximately 50% of the maternity wards in Sweden already have implemented the clinical practice with two midwives without reporting any adverse side-effects, such as increased rates of severe perineal trauma or an increase in Apgar scores <4 at five minutes, we will not perform routine interim analyses throughout the data collection. Analyses will be performed if the maternity wards notice a negative trend in outcomes related to the mother (severe perineal trauma, postpartum haemorrhage >1000 ml) or the baby (Apgar scores and neonatal resuscitation).

Clinical significance

The number of women seeking care for pelvic floor problems related to childbirth is increasing. Improving the health and well-being for women giving birth is important on a personal level but also for society. There is an ongoing debate in the Swedish media and among women regarding severe perineal trauma. Childbirth organizations are upset that care providers are not able to prevent injuries and find it extraordinary that gaps in our knowledge still exist in this field of research. Many women are afraid of giving birth vaginally because they fear an extensive tear and the consequences such a tear might have on their

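### Women are randomised at the start of the second stage although the arms differ only from the active phase, so those delivered in between enter the intention-to-treat analysis with no contrast

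*Protocol*

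**What the plan says.** The Protocol, Project design, Randomization process, fixes the time of allocation: "Randomization will take place at the start of the second stage".

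The contrast between the arms is placed later:

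- Purpose and aims describes the practice as one where "an additional midwife is present during the active phase of the second stage of labor and the birth of the baby".
- The opening of Project design has women "randomized to either having one midwife assisting the active phase of the second stage of labor and the birth of the baby", or to having two midwives present.
- The Background says that, in the practice as already used, the responsible midwife "calls for the second midwife when the active phase of the second stage has started and the presenting part of the baby is visible".

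The randomisation paragraph itself is looser and describes the intervention as "collegial presence of another midwife during the second stage".

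The Analysis section states: "The primary statistical analysis is intention to treat but a per protocol analysis will also be performed". The sample-size paragraph plans for 4.1% against 2.0%, with 1052 women per group. It raises this to 1473 for a 20% drop-out and "another drop-out of 20% for possible cases of obstetric emergencies where another midwife will be needed regardless of randomization".

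**The concern.** The document separates two moments, the start of the second stage and the start of its active phase. Allocation happens at the first, and care differs only from the second. No rule delays the opening of the envelope until the active phase.

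Some women may have a caesarean or an assisted birth in the interval. Intention to treat rightly counts them in the arm to which they were allocated, but the number of midwives in the active phase cannot have affected their outcome. They use up sample size and shrink the risk difference. Where they can have a severe tear, they also add the same risk to both arms and draw the relative risk towards 1. The Background names assisted vaginal birth as a risk factor for severe trauma, so this second route is realistic. The planned effect of 4.1% to 2.0% is not reduced for these women.

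At stake is avoidable loss of power in a trial with few events. Once women have been randomised, no analysis can recover it without exclusions after randomisation.

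**Working it through.** **Inputs from the Protocol.** Control risk is 4.1% and intervention risk 2.0%. Power is 80% and the significance level is stated as 95%. The plan needs 1052 per group and inflates this to 1473. Drop-out is 20%. A two-sided test at 0.05 is inferred, because the one-sided formula gives 829.

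**Input by assumption.** The share *f* of randomised women who never reach the active phase is not in the document. I use 2%, 5% and 10%.

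**Step 1: reproduce the plan.** With pooled variance under the null and no continuity correction, let p̄ = (4.1% + 2.0%)/2 = 3.05%. Then

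n = [1.960·√(2p̄(1−p̄)) + 0.842·√(p1(1−p1) + p2(1−p2))]² / (p1−p2)²

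= [0.4766 + 0.2043]² / 0.021² ≈ 1052 per group, as stated.

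The inflated figure is 1052 × 1.40 = 1472.8, so 1473. After the plan's 20% drop-out, 1473 × 0.80 = 1178.

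**Step 2: power with no dilution.**

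Power = Φ{[(p1−p2)√n − 1.960·√(2p̄(1−p̄))] / √(p1(1−p1) + p2(1−p2))}

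- n = 1473: Φ[(0.8060 − 0.4766)/0.2427] = Φ(1.357) = 91.3%.
- n = 1178: Φ(1.006) = 84.3%.

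**Step 3: let a share *f* have the same risk r in both arms.** The arm risks become (1−f)·4.1% + f·r and (1−f)·2.0% + f·r. The risk difference is 2.1 × (1−f) percentage points whatever r is. What r changes is the relative risk. Three values of r are used: zero (for example a caesarean), the intervention risk of 2.0%, and the control risk of 4.1%.

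| f | r | Arm risks | Relative risk | Power, 1473 per arm | Power, 1178 per arm |
|---|---|---|---|---|---|
| 0 | – | 4.10% v 2.00% | 0.488 | 91.3% | 84.3% |
| 2% | zero | 4.02% v 1.96% | 0.488 | 90.7% | 83.5% |
| 2% | 2.0% | 4.06% v 2.00% | 0.493 | 90.3% | 83.0% |
| 2% | 4.1% | 4.10% v 2.04% | 0.498 | 90.0% | 82.6% |
| 5% | zero | 3.90% v 1.90% | 0.488 | 89.8% | 82.3% |
| 5% | 2.0% | 4.00% v 2.00% | 0.501 | 88.8% | 81.1% |
| 5% | 4.1% | 4.10% v 2.11% | 0.513 | 87.8% | 79.8% |
| 10% | zero | 3.69% v 1.80% | 0.488 | 88.1% | 80.2% |
| 10% | 2.0% | 3.89% v 2.00% | 0.514 | 85.9% | 77.5% |
| 10% | 4.1% | 4.10% v 2.21% | 0.539 | 83.5% | 74.7% |

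Worked line for f = 10% and r = 4.1% at 1473: the intervention risk is 0.9 × 2.0% + 0.1 × 4.1% = 2.21%, and power is Φ[(0.7254 − 0.4845)/0.2468] = Φ(0.976) = 83.5%.

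**Step 4: a less favourable sensitivity case.** Suppose these women carry twice the control risk of the others, as might apply to assisted births, with the overall control risk held at 4.1%. The factor of two is an assumption. At f = 10% the risks are 4.1% v 2.38%, the relative risk is 0.58, and power is 75.0% at 1473 and 65.4% at 1178.

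**The case against.** **The share is unknown and may be small.** This stands. At 2% the loss is about one point at 1473 per arm. In every line of the table power at 1473 stays above the 80% target. The reply is that 1473 analysed women presuppose no drop-out. At 1178, the number left after the plan's own allowance, 5% at control risk already gives 79.8%.

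**The 20% emergency allowance should not be used as the share.** A reader might take it as the proportion lost before the active phase and obtain 73-78% power at 1473 (4.1% v 2.42%, or 3.68% v 2.0%). The document does not support this. It does not say when those emergencies occur. Those in the active phase or at the birth would still be randomised after the change and would still have no contrast. That figure cannot be put down to the timing of randomisation.

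**Caesareans do not dilute the planned effect measure.** This also stands. With zero risk in both arms the relative risk stays at 0.488, and only power falls.

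**Later opening may cost adherence.** The Background notes that wards using the practice have not added midwives. If a colleague failed to come for 10% of intervention women and they carried control risk, the contrast would again be 4.1% v 2.21% and power 83.5%. The trade-off is real, but no such rate is in the document. Some notice also remains, because the Background has the second midwife called only when the presenting part is visible as well.

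**The calling time is existing practice, and the randomisation paragraph refers to the second stage as a whole.** True, but the purpose and design sections tie the trial's own contrast to the active phase. The wording needs reconciling in any case.

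A reader might also infer that knowing the allocation early biases care in the interval, or that women will be excluded after randomisation. The document gives no mechanism for the first, and intention to treat is already the primary analysis.

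**Conclusion.** The point holds as a timing gap that the Protocol's own wording creates. Women delivered between the start of the second stage and its active phase count in the primary analysis without any possible difference between the arms. Those with no risk of the outcome cost power only; those with equal non-zero risk in both arms also pull the relative risk towards 1.

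For assumed shares of 2%, 5% and 10%, with risk between zero and the control rate, power at 1473 per arm is 90-91%, 88-90% and 84-88%, against 91% undiluted. At 1178 it is 83-84%, 80-82% and 75-80%, against 84%. Higher-risk women would make the loss larger. The true share is not in the document, so the size of the gain from a change is unknown.

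The finding does not extend to the plan's 20% emergency allowance. How women needing a second midwife in either arm are handled under intention to treat is a separate sample-size question, and moving the randomisation does not settle it.

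**What to change.** 1. Reconcile the randomisation paragraph with Purpose and aims, the Background and the opening of Project design, so that one period is named for the contrast between the arms.
2. Have the envelope opened at the start of the active phase, as close as feasible to the point where the arms diverge.
3. Log consented women who do not reach that point, with the reason. The log also supplies the share that is now unknown.
4. Keep every randomised woman in the intention-to-treat analysis.

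The cost is one sentence in the randomisation section and a screening log. The downside is shorter notice for the ward to free a second midwife.

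### The envelope code contains a group letter that is not stated to be hidden until opening, and one fixed block size of ten is printed for an unblinded trial: a cheap tightening of concealment, not a demonstrated breach

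*Protocol*

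**What the plan says.** All the design facts are in the Protocol, Project design, under the randomisation process. Allocation is 1:1.

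- **Envelopes:** "Sealed and opaque envelopes will be used and will be prepared with a unique code". The code consists of a site letter, then "a second code letter identifying which group it belonged to (intervention or control) followed by a consecutive number". The paragraph does not say whether the code is on the outside or only inside, whether the number runs across both arms or within each, or that envelopes are opened in order.
- **Blocks:** "block randomization in blocks of ten will be used". No variation in size is mentioned, nor whether blocks are kept within site.
- **Blinding, timing and person:** "It will not be possible to blind either women or midwives in this study"; "Randomization will take place at the start of the second stage"; "The midwife in charge will be responsible for the randomization process". It is not stated whether the midwife in charge also attends the birth.

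The data collection paragraph puts the woman's allocation code on the midwives' questionnaires as well. The Background says of wards already using two midwives: "The maternity wards that practise this method have not increased the number of midwives". It also says: "Traditionally midwives have asked colleagues for a second opinion or to assist in complicated situations".

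**The concern.** Sealing and opacity protect what is inside an envelope. They do not protect a code written on the outside, and here the code carries the arm. Separately, when staff see each allocation as it is made and know that every block holds five of each arm, the rest of a block is known once one arm has had its five.

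Someone who can foresee an allocation can hold a woman back. The Background supplies possible motives in both directions: a second midwife may be avoided where staffing has not grown, or sought for births expected to be difficult. The direction of any bias is therefore open. Intention to treat does not repair selection that happens before randomisation. The baseline adjustment in the Analysis section would help only for measured factors.

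**Working it through.** **Inputs from the protocol.** Block size 10, allocation 1:1, four sites, tear risk 4.1% against 2.0%, 1473 women per group, 2946 in total.

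**The plan's own figure.** The protocol gives no figure for predictability. The total used below as denominator does reproduce. With a two-sided 5% level, 80% power, pooled variance and no continuity correction, n = [1.960 × √(2 × 0.0305 × 0.9695) + 0.842 × √(0.041 × 0.959 + 0.02 × 0.98)]² / 0.021² gives 1052 per group. Then 1052 × 1.4 = 1472.8, so 1473 per group and 2946 in total.

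**Full tracking, blocks within site (assumed).** An allocation is certain beforehand if all five of the other arm have already been used. Each of the ten places has probability 1/6 of falling after all five of the other arm, so 10/6 = 1.67 places per block are certain, or 16.7%. Enumeration of all 252 orders gives the same. 2946/6 = 491 women.

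**Partial tracking.** Let p be the share of allocations that a person sees, with independent sightings (assumed; shift work would cluster them).

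- Number running across both arms: the block end shows at every tenth envelope, but all five allocations of the exhausted arm must have been seen. Share = p^5/6.
- Number running within each arm, running total known: seeing the fifth code of the exhausted arm is enough. Share by that route = p/6.

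| p | Across arms, p^5/6 | Within arm, p/6 |
|---|---|---|
| 1 | 16.7% (491) | 16.7% (491) |
| 0.75 | 4.0% (117) | 12.5% (368) |
| 0.5 | 0.5% (15) | 8.3% (about 246) |

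**Blocks across the four sites.** If a ward sees only its own quarter and the number runs across arms, the share is 0.25^5/6 = 0.016%, fewer than one woman in 2946.

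**Size of bias at the 16.7% upper bound, no true effect.** These assumptions are not in the protocol: 20% of women have three times the tear risk of the rest, and half to all of them are held back whenever the unwanted arm is certain.

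- Risk in low-risk women: 4.1 / (0.8 + 0.2 × 3) = 2.93%.
- All held back: 0.8333 + 0.1667 × (2.93/4.1) = 0.952; in the opposite direction 1/0.952 = 1.050.
- Half held back: high-risk women are 0.1/0.9 = 11.1% of those entered, so the risk is 2.93 × (0.889 + 3 × 0.111) = 3.58%. Then 0.8333 + 0.1667 × (3.58/4.1) = 0.979; in the opposite direction 1.022.

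**Against sampling error.** With 1473 per arm at 4.1%, SE(log RR) = √(2 × 0.959 / (1473 × 0.041)) = 0.178. The worst case above, |log 0.952| = 0.049, is just under 0.3 of a standard error. It would raise the two-sided type I error from 5.0% to about 5.9%.

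**Effect of varying sizes.** With blocks of 8, 10 and 12 in random order, and an observer who sees everything and knows the set of sizes, simulation gives 1.2% certain. The same worst-case illustration then gives 0.997 or 1.003. Naming the arm that is behind is right 65.3% of the time with fixed tens and 65.2% with the mix.

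**The case against.** A reader might infer that the arm can be read from the unopened envelope, so that all 2946 allocations are open. The document does not support that. It calls the envelopes sealed and opaque, and an arm printed outside would defeat that purpose. The data collection paragraph speaks of the code as something the woman receives on allocation, which fits a card found on opening. Neither point settles where the code is printed. What stands is a silence that one sentence would close. A separate envelope procedure may exist, but this paragraph does specify the code and the block size, and neither is a matter for an analysis plan.

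A reader might also take 16.7% as the expected leak. It is an upper bound: it needs blocks within site and one person who sees every allocation and counts. The role of midwife in charge may be shared across shifts. If blocks run across sites and the number runs across arms, the problem all but vanishes.

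The mechanism is inferred as well. Re-ordering needs two eligible women to reach the second stage close together, which limits it; holding one woman back stays possible. The staffing remark in the Background concerns wards already using the practice, not the trial sites, and no avoidance is reported. Finally, varying the block size leaves the roughly 65% guessing rate unchanged. All of this stands, and it makes the point smaller without removing it.

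**Conclusion.** The point holds as a cheap improvement, not as an error that the text demonstrates. The protocol puts the arm in the envelope code without saying that it is hidden until opening, and it publishes one fixed block size in a trial where staff see every allocation made around them.

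Broken concealment is not shown. If concealment holds, the remaining predictability is at most 16.7%, provided that blocks are within site. With partial tracking it depends strongly on the numbering: at half the allocations seen, 0.5% or 8.3%. The plausible bias is modest, with a relative risk of about 0.95 to 1.05 at the upper bound on the stated illustrative assumptions and no predictable direction. That is small beside the targeted fall from 4.1% to 2.0%. Confidence is medium, because the code's position, the numbering scheme and the level of blocking are all unstated.

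**What to change.** Make two changes together in the randomisation paragraph.

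1. Replace the description of the code with: *The outside of each envelope carries only the site letter and one consecutive number running across both arms. The group appears only on the card inside the sealed, opaque envelope. Envelopes are opened in numerical order.*
2. Replace the fixed block size with randomly varying sizes, generated away from the wards, not disclosed to them and not printed in the protocol. Sizes such as 8, 10 and 12 cut certain allocations from at most 16.7% to about 1%, even for someone who learns the set.

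They belong together because a single running number combined with fixed tens would mark every block end.

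The cost is a new list, relabelling of unused envelopes and two protocol sentences, with no extra staff and no change in sample size. The limits are that guessing the arm that is behind stays right about 65% of the time for someone who follows the whole sequence, and that the change does not blind those who handle the midwives' questionnaires.
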